1.1 Protocol Synopsis

Title	A Prospective Analysis of the Use of GENTRIX® Surgical Matrix for Soft Tissue Reinforcement in Ventral Hernia Repair as Long Term Follow Up (LTFU) to T-GENVIH-002 study
Short Title	GENTRIX Ventral Hernia Repair LTFU study
Protocol Number	T-GENVIH-003
Study Description	The purpose of this study is to collect additional safety data and demonstrate the performance of Integra GENTRIX® Surgical Matrix for reinforcement of ventral hernia repairs from a sub-population of participants in the T-GENVIH-002 study, specifically those with laparoscopic or robotic repair. Prospective data will be collected and assessed for later post-operative surgical site events and complications in the post-operative period from the last timepoint of data collection in T-GENVIH-002 to present.
Pre/Post-Market	Post-Market
Product(s)	GENTRIX® Surgical Matrix - (6-layer), - Plus (8-layer), and -Thick *Refer to APPENDIX I at the end of the protocol for product-specific Stock Keeping Units (SKUs) to be included in this study.
Indications for Use	GENTRIX® Surgical Matrix is intended for implantation to reinforce soft tissue where weakness exists in patients requiring gastroenterological or plastic & reconstructive surgery. Reinforcement of soft tissue within gastroenterological and plastic & reconstructive surgery includes, but is not limited to, the following open or laparoscopic procedures: hernia (e.g., hiatal/ diaphragmatic) and body wall repair, colon and rectal prolapse repair, tissue repair, and esophageal repair. GENTRIX® Surgical Matrix minimizes tissue attachment to the device in case of direct contact with viscera.
Study Design	Single-Arm, Prospective, Single-Center
Study Rationale	This study adds to the available data evaluating the safety and effectiveness of GENTRIX® Surgical Matrix in ventral hernia repair, particularly in a real-world population and particularly in the sub-

	population of minimally invasive surgery (MIS) cases (i.e., laparoscopic and robotic) from the GENVIH-002 study.
Primary Objective	The primary objective of this study is to capture additional existing clinical performance data to confirm the continued performance of the Gentrix® Surgical Matrix over longer term.
Safety Objective	The safety objective is to capture existing Gentrix® Surgical Matrix Complication data in the longer term period post primary repair procedure, not previously reported in T-GENVIH-002 study. Gentrix® Surgical Matrix Complications are defined but not limited to: 
 • Seroma • Abscess • Dehiscence • Hematoma • Wound necrosis • Ileus • Fistula • Delayed wound healing
Primary Endpoint	1. Incidence of clinically confirmed recurrence of the primary hernia to date, including not previously reported in T-GENVIH-002 study.
Secondary Endpoints	1. Incidence of self-reported recurrence (i.e., bulge) of the primary hernia to date, including not previously reported in T-GENVIH-003 study. 2. Incidence of Surgical Site Occurrences requiring Procedural Intervention (SSOPI) of the primary hernia repair to date, including not previously reported in T-GENVIH-002. 3. Incidence of Surgical Site Occurrences (SSOs) of the primary hernia repair to date (seroma, abscess, dehiscence, hematoma, wound necrosis, ileus, fistula, delayed wound healing), including not previously reported in T-GENVIH-002 study. 4. Incidence of Surgical Site Infections (SSIs) post primary hernia repair to date, including not previously reported in T-GENVIH-002 study.

	5. Incidence of reoperation requirement of the primary hernia repair to date, including not previously reported in T-GENVIH-002 study.
Description of Study Intervention	A one-off subject interview with questionnaire will include a series of patients who underwent abdominal wall reconstruction for a ventral hernia repair with Integra GENTRIX® Surgical Matrix to date, including not previously reported in the T-GENVIH-002 study.
Study Population	Patients from the sub-population of minimally invasive surgical approach (e.g., laparoscopic or robotic) of the T-GENVIH-002 study.
Inclusion Criteria	
 Patient was a subject in the T-GENVIH-002 study and underwent minimally invasive (i.e., laparoscopic or robotic) abdominal wall reconstruction for a primary hernia using Integra GENTRIX® Surgical Matrix. Subject has participated in the informed consent process and signed a study-specific informed consent document. Subject is fluent in US English or US Spanish language. Subject is willing to complete an e-consent and phone or in-office visit.
Exclusion Criteria	Not applicable.
Description of Sites/Facilities Enrolling Participants	One site located in the United States (US) will participate in this study.
Study Duration	Approximately three months.
Study Visits/Schedule of Study Activities	This prospective study specifically aims to collect data from the day of the primary hernia surgical repair procedure longer term post-operatively to date, including not previously reported in T-GENVIH-002 study.
Data Collection	Data will be collected via a phone visit and questionnaire administered by the study coordinator (or, in the alternative, an in-office visit and questionnaire administered by the study coordinator) and entered into an electronic data capture system by the site. The following data will be collected on the Long Term Follow Up (LTFU) of the primary hernia repair.

	Clinical Performance and Safety Evaluation: 
 1. SSOPI 2. SSO(s) 3. SSI(s) 4. Hernia Recurrence 5. Reoperation(s) 6. Adverse Event(s)
Statistical Methods & Analyses	
Study outcomes will be summarized using descriptive statistics. Categorical variables will be summarized using frequencies and percentages. Continuous variables will be summarized using means, standard deviations, medians, quartiles, ranges, and numbers of observations.
 
Statistical analysis will be based on data from all evaluable subjects meeting the eligibility criteria.

1.2 Schedule of Data Collection Activities

Table 1: Schedule of Data Collection Activities

	Screening	Subject Visit 1
*Prospective Data Collection		
Eligibility/Consent	X	
Complete Case Report Form(s)	X	X
¥Adverse Events	X	X

*May occur on separate days

¥Primary hernia surgery

2 Introduction

2.1 Background

Ventral hernias are a type of abdominal hernias that can occur at any location along the vertical abdominal wall. Typically, these defects are acquired resulting from complications of a prior surgery, trauma, or natively weak points of the abdominal wall in some individuals. Obesity may contribute in large part to the weak points due to cyclic patterns of weight gain and loss. One in eight patients will develop an incisional hernia after abdominal surgery¹.

Ventral hernia repair is one of the most common surgical procedures performed in the United States. Every year there are approximately 350,000 repairs performed in the US with an estimated cost of \$3.2 billion.² Different patient populations require different solutions in order to make a repair as cost-effective and risk-averse as possible.

Clinical evidence has shown that primary suture repair of a ventral hernia alone results in high recurrence rates (>50%), and that all incisional hernia repairs should be reinforced with surgical mesh.^{3,4} Despite this consensus, due to the large variety of surgical meshes available currently, there is a lack of consensus on the ideal material for each repair. Ventral hernia treatment decisions are typically tied to patient operative risk, symptomatic concerns, and potential clinical complications of the repair.

Permanent synthetic mesh has been the standard of care in the reinforcement of simple, clean hernias due to its minimal cost and history of low recurrence.^{5,6} However, due to the inherent permanence, long-term complications such as product migration, contraction, erosion, and infection are common.⁵⁻⁸ In the complex hernia setting, synthetic materials may not be ideal due to the increased risks of surgical site occurrences (SSOs) and resulting recurrences.⁵⁻⁸ These complications can prove costly with each hernia recurrence and wound event estimated to cost an additional \$44,000 and \$85,000 respectively.^{9,10} Specifically, a mesh infection can cost up to \$140,000 and may require explantation of the mesh altogether.¹⁰

Biologically-derived materials, such as acellular dermal matrices, were developed for use in complex hernia repair to mitigate some of the risks seen with synthetic materials. However, long-term study of these materials demonstrated a 31.8% recurrence rate and 36.6% wound infection rate at 18.2 months follow-up.¹¹

Approximately 74% of inpatient ventral hernia repairs are completed as open procedures. While this number is slightly lower for outpatient ventral hernia repairs (64%), this remains the predominant surgical approach¹² likely for more complex cases.

Currently available biologically derived mesh options for reinforced repairs include a class of non-dermal products including Gentrix® Surgical Matrix devices.

This post-market clinical study is being conducted to characterize the performance and safety of Gentrix® Surgical Matrix -(6-layer), -Plus (8-layer) and -Thick devices in the repair of ventral hernias in patients between 22 years and 80 years old (inclusive) at the time they underwent abdominal wall reconstruction utilizing Gentrix® Surgical Matrix as a reinforcement graft during the time period post primary hernia surgical repair to date, not previously reported in T-GENVIH-002, as a *longer term follow-up* of safety and performance data in the sub-population of minimally invasive surgical cases (i.e., laparoscopic and robotic).

2.2 Investigational Product Overview

Gentrix® Surgical Matrix is intended for implantation to reinforce soft tissue where weakness exists in patients requiring gastroenterological or plastic & reconstructive surgery.

Reinforcement of soft tissue within gastroenterological and plastic & reconstructive surgery includes, but is not limited to, the following open or laparoscopic procedures: hernia (e.g., hiatal/diaphragmatic) and body wall repair, colon and rectal prolapse repair, tissue repair, and esophageal repair. Gentrix® Surgical Matrix minimizes tissue attachment to the device in case of direct contact with viscera.

The Gentrix® Surgical Matrix Device configuration includes the Gentrix® Surgical Matrix (6-layer), Gentrix® Surgical Matrix Plus (8-layer), and the Gentrix® Surgical Matrix Thick.

2.2.1 Gentrix® Surgical Matrix (6-layer):

Gentrix® Surgical Matrix (6-layer) is composed of a porcine-derived extracellular matrix, also known as urinary bladder matrix. The device is supplied in a multilayer sheet configuration in sizes up to 10 cm x 15 cm and packaged in double peel-open pouches. The device is terminally sterilized using electron beam irradiation.

[figure not shown]

Figure 1: Gentrix® Surgical Matrix (6-layer)

2.2.2 Gentrix® Surgical Matrix Plus (8-layer):

Gentrix® Surgical Matrix Plus (8-Layer) is composed of porcine-derived extracellular matrix, also known as urinary bladder matrix. The device is supplied in a multilayer sheet configuration in sizes up to 10 cm x 15 cm and packaged in double peel-open pouches. The device is terminally sterilized using electron beam irradiation.

[figure not shown]
[figure not shown]

Figure 2 : Gentrix® Surgical Matrix Plus (8-layer)**2.2.3 Gentrix® Surgical Matrix Thick:**

Gentrix® Surgical Matrix Thick is composed of a porcine-derived extracellular matrix, also known as urinary bladder matrix. The device is supplied in a multi-layer sheet configuration in sizes up to 30 cm x 40 cm and packaged in double peel-open pouches. The device is terminally sterilized using electron beam irradiation. Animal studies have shown device resorption in approximately 240 days.

**Figure 3 : Gentrix® Surgical Matrix Thick****2.2.1 Study Device Intended Purpose**

The Gentrix® Surgical Matrix devices were used within label in this prospective study. There were no specific medical or surgical procedures involved in the use of the study devices, other than the standard of care. A full description of the medical and surgical procedures related to the Gentrix® Surgical Matrix devices is available in the Instructions for Use (IFU).

2.2.2 Study Device Contraindication

Patients with known sensitivity or allergy to porcine materials.

2.2.3 Required Training and Experience

Previously trained on the use of the devices, the investigator must have used the devices within label in this study. Integra LifeSciences Corporation did not train, nor dictate, the surgery

T-GENVIH-003 study

Confidential

Protocol Version: V1.0 dated 02AUG2023

Page 17 of 41

This document contains proprietary and confidential information of Integra LifeSciences Corporation. Integra's confidential information may not be used, disclosed or reproduced without the prior written consent of Integra LifeSciences Corporation.

technique(s). The investigator must meet certain expectations per Sponsor Standard Operating Procedures (SOPs).

2.2.4 Device Accountability

No device accountability will be performed for the purposes of this study given the study is noninterventional.

2.2.5 Device Traceability

No device traceability will be performed for the purposes of this study given the study is noninterventional.

2.3 Study & Design Rationale

This is a single-arm, single-center, prospective study to collect in routine use additional safety data and demonstrate the performance of Integra Gentrix® Surgical Matrix for reinforcement of minimally invasive (i.e., laparoscopic and robotic) ventral hernia repairs as a LTFU of the T-GENVIH-002 study. Routine use data to date – longer term, not previously reported -- will be collected prospectively at one site. This study adds to the available data evaluating the safety and effectiveness of Gentrix® Surgical Matrix in ventral hernia repair, particularly in a real-world population, and particularly in the sub-population described.

3 Objectives and Endpoints

3.1 Primary Objective

The primary objective of this study is to capture existing clinical performance data to confirm the continued performance of the Gentrix® Surgical Matrix as a long term follow up (LTFU) to T-GENVIH-002 study for minimally invasive surgical approach (laparoscopic and robotic) sub-population of cases post primary hernia surgical repair to date, not previously reported in the T-GENVIH-002 study.

Existing clinical data support the safety and performance of the Gentrix® Surgical Matrix. There are currently no safety concerns with these products. This clinical investigation will confirm the safety and performance of the Gentrix® Surgical Matrix particularly in MIS cases and identify any unknown or not previously reported side-effects.

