5.5 Strategies for Recruitment

A one-off subject phone (call) visit will constitute the source of data and will be collected using a study-specific eCRF delivered via a phone script by the site responsible or their designee(s). Each patient should be included in the study only once. Patient screening will rely on site identification and contact of prior T-GENVIH-002 study subjects (Sponsor remains blinded) and e-consent process. In these cases, every effort should be made to identify every possible eligible patient. For those that are lost to follow up, site may work directly with a Sponsor approved people search service (Sponsor remains blinded). In order to be eligible for the study, patients should meet all of the eligibility criteria.

For subjects who decline an electronic consent collected remotely, an in-office interview and assistance with completing the electronic consent in person with the site study coordinator or their designee(s) will be offered for the convenience of the subjects and to maximize data collection efforts.

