7.2 Reporting of Safety Information

7.2.1 Non-Reportable Event

Adverse Events not related to the primary hernia repair procedure will not be required to be reported by the investigator in this study.

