10.1 Statistical Hypotheses

This is a prospective, single-arm, single center post-market study to capture existing clinical performance data to confirm the continued performance of the GENTRIX® Surgical Matrix. A formal hypothesis does not apply to this study. Subjects from that consecutive series will be included in the study based on the defined inclusion and exclusion criteria.

T-GENVIH-003 study

Confidential

Protocol Version: V1.0 dated 02AUG2023

Page 35 of 41

This document contains proprietary and confidential information of Integra LifeSciences Corporation. Integra's confidential information may not be used, disclosed or reproduced without the prior written consent of Integra LifeSciences Corporation.

Primary Endpoint(s):

The primary endpoint of this prospective study is to determine the incidence of clinically confirmed recurrence of the primary hernia to date, including not previously reported in T-GENVIH-002 study.

Secondary Endpoint(s):

1. Incidence of self-reported recurrence (i.e., bulge) of the primary hernia to date, including not previously reported in T-GENVIH-003 study.
2. Incidence of Surgical Site Occurrences requiring Procedural Intervention (SSOPI) of the primary hernia repair to date, including not previously reported in T-GENVIH-002.
3. Incidence of Surgical Site Occurrences (SSOs) of the primary hernia repair to date (seroma, abscess, dehiscence, hematoma, wound necrosis, ileus, fistula, delayed wound healing), including not previously reported in T-GENVIH-002 study.
4. Incidence of Surgical Site Infections (SSIs) post primary hernia repair to date, including not previously reported in GENVIH-002 study.
5. Incidence of reoperation requirement of the primary hernia repair to date, including not previously reported in GENVIH-002 study.

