10.2 Sample Size Determination

Subjects from that consecutive series will be included in the study based on the defined inclusion and exclusion criteria. The planned sample size for this study will be approximately 21 treated subjects.

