8. SAMPLE SIZE DETERMINATION

Subjects from that consecutive series will be included in the study based on the defined inclusion and exclusion criteria, the subgroup of T-GENVIH-002 subjects underwent Laparoscopic or Robotic surgery. The sample size is not based on hypothesis testing. The planned sample size for this study will be approximately 21 treated subjects.

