9. STATISTICAL ANALYSES

9.1 General Statistical Considerations

Descriptive statistics will be used to summarize study outcomes. No formal statistical testing will be performed. The study objectives will be presented by summary statistics.

For categorical data, frequencies and percentages will be provided. For continuous data, descriptive statistics, including sample size, mean, median, standard deviation, and range of values (i.e., minimum, and maximum values) will be provided.

A separate Table Listing Graphs (TLFs) will be provided.

All statistical analysis will be conducted using SAS® for Windows, version 9.4 or later.

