11. MISSING DATA

Reasonable efforts will be made to obtain complete data for all subjects. Nevertheless, given the nature of this study (i.e. Retrospective), it is anticipated that missed visits/evaluations will occur and hence there will be missing data on some of the endpoints. Missing data will not be imputed.

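### Protocol 3.1 promises to confirm safety and identify any unknown side-effect, which about 21 subjects interviewed once cannot support for uncommon effects

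*Protocol*

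**What the plan says.** The second paragraph of Protocol 3.1 first says that existing data support the device and that no safety concerns are known. It then says that this investigation will confirm safety and performance "particularly in MIS cases and identify any unknown or not previously reported side-effects". It attaches no frequency, probability or limit to that statement.

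Protocol 10.2 gives the size: "The planned sample size for this study will be approximately 21 treated subjects". SAP 8 repeats the number and adds "The sample size is not based on hypothesis testing". The 21 are the laparoscopic and robotic subgroup of T-GENVIH-002. Protocol 10.1 states "A formal hypothesis does not apply to this study", and SAP 9.1 states "No formal statistical testing will be performed".

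On data collection, Protocol 5.5 says "A one-off subject phone (call) visit will constitute the source of data", with an in-office interview as the alternative. On completeness, SAP 11 says "it is anticipated that missed visits/evaluations will occur" and rules out imputation.

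Protocol 10.4.5 and SAP 9.3.4 summarise adverse events by frequency and percentage. Neither document plans a confidence interval or states what event frequency the study could detect.

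The formal safety aims are narrower than the sentence in 3.1. Protocol 3.2 aims to capture later complications, and SAP 3.3 aims to report their incidence, in both cases those not previously reported in T-GENVIH-002.

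**The concern.** The sentence in 3.1 says what the study will do, and its object is any unknown side-effect. A study of about 21 people is more likely than not to miss an effect that occurs in 1% or 2% of patients, so the sentence does not follow from the design.

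The planned output does nothing to correct it. If no new side-effect is recorded, the tables show a bare zero and 0%, next to an objective that speaks of confirming safety and finding anything unknown. Nothing on the page would tell the reader that a zero from 21 subjects still leaves room for a rate above one in ten.

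**Working it through.** **Inputs.** n = 21 (Protocol 10.2, SAP 8). The documents give no alpha, power, target precision or expected event rate, so there is no sponsor figure to reproduce. The calculation treats subjects as independent with a common true rate p, and assumes that every case is captured at interview.

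**Chance of at least one case.** P = 1 − (1 − p)^21.

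| True rate p | (1 − p)^21 | P(at least one case) |
|---|---|---|
| 1% | 0.810 | 19.0% |
| 2% | 0.654 | 34.6% |
| 5% | 0.341 | 65.9% |
| 10% | 0.109 | 89.1% |

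**Rate that would be seen with a given probability.** Setting (1 − p)^21 = 1 − P and solving for p:
- P = 95%: p = 1 − 0.05^(1/21) = 0.1329, or 13.3%
- P = 90%: p = 1 − 0.10^(1/21) = 0.1038, or 10.4%
- P = 80%: p = 1 − 0.20^(1/21) = 0.0738, or 7.4%

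**What zero cases in 21 would exclude.** The one-sided 95% upper limit solves the same equation as the 95% line above and is 13.3%. The two-sided exact (Clopper-Pearson) 95% limit is 1 − 0.025^(1/21) = 0.1611, or 16.1%. As a rough check, the rule of three gives 3/21 = 14.3%.

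**If fewer take part.** The documents expect missing data but give no rate, so the following numbers of participants are assumptions. The 95% threshold, 1 − 0.05^(1/n), is 14.6% at n = 19, 16.2% at n = 17 and 18.1% at n = 15.

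**Scale.** From n = ln 0.05 / ln(1 − p), rounded up, a 95% chance of at least one case needs 59 subjects at 5%, 149 at 2% and 299 at 1%. These figures show the distance between wording and design. They are not a proposed sample size.

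**The case against.** The best defence is that the sentence states an aim. In these documents, not previously reported generally means not reported in T-GENVIH-002 for these same people. The site must identify the full consecutive series (Protocol 6.1.1). On that reading, the sentence promises only to record whatever new events this closed cohort has had, and a binomial detection probability for a wider population answers a different question. The formal objectives in Protocol 3.2 and SAP 3.3 are already modest, and SAP 3 does not carry the phrase about unknown side-effects. Both documents disclaim hypothesis testing. The eligible pool is fixed, and a descriptive study need not be powered.

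Much of this stands. A reader might infer that the documents contain a miscalculation, or that the study is too small. Neither is supported: no detection probability or precision is claimed that could be wrong, and enrolling the whole available subgroup is reasonable. The 95% benchmark is chosen for this review and is not in the plan.

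A reader might also infer that most safety lines will be zero and will be reported as proof of safety. The documents give no expected event rates and do not say how a zero would be worded.

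Nor should much weight be put on the reporting exemption in Protocol 7.2.1: "Adverse Events not related to the primary hernia repair procedure will not be required to be reported by the investigator in this study". It could remove an effect whose link is not yet recognised. However, 7.3.1 requires every potentially device- or procedure-related event to be reported, and 7.2.3 classes cases that cannot be assessed as possibly related.

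The aim reading does not remove the point. The sentence also speaks of confirming safety and of unknown effects, which goes beyond recording events in 21 people. Nothing in either document limits it, and no interval is planned that would let a reader limit it.

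**Conclusion.** The point holds as one about wording and reporting. Protocol 3.1 claims more than about 21 subjects interviewed once can support for uncommon side-effects, and safety summaries made up only of counts and percentages leave the claim unqualified.

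The conclusion does not depend on the benchmark. At 95% the threshold is 13.3%, at 80% it is still 7.4%, and a 1% effect would be missed about four times in five (81.0%). These figures assume that all 21 take part and that every case is captured. Any shortfall in either raises the threshold.

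No planned analysis depends on the sentence, and sample size, data collection and endpoints can stay as they are. The change is still worth making, because it costs very little and exact limits tell the reader more than bare percentages.

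**What to change.** 1. **Protocol 3.1.** Replace the claim to confirm safety and identify unknown effects with wording such as: *describe any side-effects observed in the enrolled subjects that were not previously reported in T-GENVIH-002*. This keeps the search for new events and agrees with Protocol 3.2 and SAP 3.3.
2. **Protocol 10.2 and SAP 8.** Add: *With 21 subjects, zero observed events is compatible with a true rate of up to 13.3% (one-sided 95% limit) or 16.1% (two-sided exact 95% limit).*
3. **SAP 9.3.4.** Report exact 95% Clopper-Pearson limits, with the number actually interviewed as denominator, for the summary lines (any related AE, any SADE, any unanticipated or not previously reported event). Do the same for each complication pre-listed in Protocol 3.2, zero counts included. The limits must sit on these lines because an unknown effect that never occurs has no row of its own in a table of reported events.

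The cost is a few more table columns and a stated capability that looks less favourable. No additional subjects or visits are needed.
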